3.4. Study Termination

This study may be prematurely terminated, if in the opinion of the Investigator (at a participating site) or Rhythm (for the whole study), there is sufficiently reasonable cause. The terminating party will provide written notification documenting the reason for study termination to either the Investigator or Rhythm.

Circumstances that may warrant termination include, but are not limited to:

- Determination of unexpected, significant, or unacceptable risk to patients.
- Failure to enter patients at an acceptable rate. This is particularly important, as the number of patients hoped to enroll in this study represents a substantial portion of all already identified patients worldwide.
- Insufficient adherence to protocol requirements.
- Insufficient complete and/or evaluable data.
- Plans to modify, suspend or discontinue the development of the study drug.

Should the study be closed prematurely, all study materials must be returned to Rhythm or designee and Rhythm will notify the applicable competent authorities and ethics committees as per ICH E6 R2 and the EU Clinical Trials Directive (2001/20/EC).

In addition, it is still unclear how many patients will be required in a pivotal study to assess the safety and efficacy of setmelanotide in *LEPR* deficiency patients, an ultra-rare condition. Therefore, this study may be terminated when Rhythm, in consultation with regulatory authorities, determines that there is sufficient patient data to support the potential application for registration of this drug for an indication in *LEPR* deficiency obesity.

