**Trial Design**

This is a pivotal study to assess long-term (~1 year) efficacy of setmelanotide in LEPR deficiency obesity. The study will begin with an initial period of dose titration lasting between 2 and 12 weeks where the individual patient's therapeutic dose will be established by upwards dose titration in 2-week intervals. Thereafter, patients will continue active treatment at their individually titrated optimal therapeutic dose for an additional 10 weeks, for a total combined dosing duration of 12 weeks at the individual patient's therapeutic dose [i.e., the last 2 weeks during dose titration plus 10 weeks of open label treatment]. For patients who demonstrate at least 5 kg weight loss (or at least 5% weight loss if baseline body weight < 100 kg) at the end of the Open Label Treatment Period, they will continue onto the double-blind, variably-timed, placebo-controlled, withdrawal period lasting 8 weeks inclusive of a 4-week period of placebo treatment. The onset of the placebo period will be variable for each patient to mask the actual

timing of the withdrawal period. Following the 8-week withdrawal period, patients will continue dosing at their therapeutic dose for ~32 weeks, resulting in a total of ~52 weeks dosing at their therapeutic dose.
 
Where feasible, and for patients who agree to participate, there
 

Study Population
 
Male and female patients, 6 years of age and above, with a confirmed diagnosis of LEPR Deficiency Obesity due to bi-allelic, loss-of-function LEPR gene mutations.

Number of Patients & Study Centers
 
It is currently anticipated that a total of ~10 patients will be enrolled in this study. The total number of patients required for registration is yet to be confirmed with applicable regulatory authorities, given that true prevalence of this ultra-rare disease is uncertain. Therefore, the total number of patients may be increased or decreased to satisfy regulatory requirements for registration, depending upon the total number of affected patients identified.
 
It is anticipated that up to 10 centers located worldwide will participate in this study. If added patients are to be enrolled, additional sites may be added, as necessary.

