Study Drug and Administration	
All study drugs are for investigational use only and are to be used only within the context of this protocol. All investigational study drugs (setmelanotide and placebo) will be supplied by Rhythm.
 
Setmelanotide drug product (RM-493-mPEG/DSPE formulation) is a sterile solution for injection. The product is manufactured at a concentration of 10.0 mg/mL.
 
Placebo will be vehicle.
 
Setmelanotide and placebo will be administered as subcutaneous (SC) injection once daily.
 
There will be extensive training of patients in drug administration including educational materials. Study specific training materials will be provided to both the investigative staff and study participants and caregivers. Rhythm will provide extra placebo supplies for use during training.

Statistical Considerations	
The objective of this study is to demonstrate statistically significant and clinically meaningful weight loss in patients with LEPR deficiency obesity after ~1 year of treatment.
 
As patients remain on treatment for 1 year, more weight loss is expected.
 
The primary endpoint is proportion of patients in the FAS who demonstrate at least 10% weight loss at ~1 year (10-14 months post baseline) compared to baseline. Patients with missing data after 10 months from baseline will be counted as not having 10% weight loss at 1 year. The primary research hypothesis is that this proportion is at least 5%. The null hypothesis is that this proportion is at most 5%. Since prior data on untreated LEPR deficient patients suggests none will have 10% weight loss at 1 year without intervention, the 5% assumed null hypothesis value is conservative.
 
It is expected that treatment with RM-493 for 1 year is associated with a TRUE underlying probability of at least 10% weight loss at 1 year of at least 50%. That assumption yields at least 94% power to yield a statistically significant ($\alpha=0.05$ and 0.025 1-sided, due to discreteness of the binomial distribution) difference from the null hypothesis 5% value for $N=10$ FAS patients. If the TRUE probability of at least 10% weight loss at 1 year is 40%, then power is ~83%. The

minimum OBSERVED proportion of N=10 patients with at least 10% weight loss at 1 year that would yield statistical significance (alpha=0.05 and 0.025 1-sided, due to discreteness of the binomial distribution) is 0.3 (3 of 10).

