2. STUDY OBJECTIVES AND ENDPOINTS

2.1. Study Objectives

LEPR deficiency obesity is an ultra-rare genetic condition characterized by severe early onset obesity and profound hyperphagia (characterized by patients as increased appetite and hunger with impaired satiety) with numerous comorbidities, and likely early mortality. To our knowledge through patient identification efforts, there have been less than 50 cases currently described in the literature, with most cases diagnosed as children. Therefore, we anticipate patient identification to be challenging and are targeting enrolling at least 10 individuals (pediatric, adolescents and/or adults), mostly from among already identified patients, to assess the safety and efficacy of setmelanotide in patients with LEPR deficiency obesity. Given the rarity and unmet need of LEPR deficiency and the initial compelling results in the first LEPR patients and the two POMC deficiency obesity patients treated, a conventional placebo controlled trial is not likely to be feasible. Due to the ultra-rare prevalence of LEPR deficiency obesity, if additional patients are identified beyond the target enrollment of 10, they may be enrolled.

The objective of this study is twofold; first, to assess safety and efficacy of setmelanotide after 1 year of chronic treatment. Secondly, since there are so few patients with LEPR deficiency available, and this study is an open label design, evidence of drug effect will be sought within each patient's course of treatment. Therefore, each patient will participate in a short, double-blind placebo-controlled withdrawal period that will allow patients to serve as their own control to assess any reversal effects on weight and hunger to confirm any drug effects.

[figure not shown]
2.1.1. Primary Objective:

- To demonstrate statistically significant and clinically meaningful effects of setmelanotide on percent body weight change in patients with LEPR deficiency obesity due to rare bi-allelic or loss-of function mutations at the end of 1 year of treatment.

2.1.2. Secondary Objectives:

To assess the effect of setmelanotide, over one year, on:

- Safety and tolerability of setmelanotide (including BP and HR).
- Hunger for patients ≥ 12 years old.
- Percent change in body fat mass.
- Glucose parameters: fasting glucose, glycated hemoglobin (HbA1c), oral glucose tolerance test (OGTT) with focus on parameters of insulin sensitivity.
- Waist circumference.

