4. STUDY POPULATION

4.1. Number of Patients

It is currently anticipated that at least 10 patients will be treated for ~1 year with setmelanotide. Given the ultra-rare incidence of the disease, if additional patients are identified, they may be enrolled as available to gain additional experience. The study population will include obese males and females that are at least 6 years old with confirmed diagnosis of bi-allelic or loss-of-function *LEPR* loss of function gene mutation.

Given this study involves participants <18 years of age, measures should be taken to reduce pain and distress in this younger population. Considerations for the study staff are included in Appendix 11.11.

The specific inclusion and exclusion criteria for enrolling patients in this study are presented in the section below. As these patients are ultra-rare, any criteria not fulfilled will be reviewed with Rhythm. Assuming no severe health concerns, a joint determination will be made regarding the acceptability of enrolling patients not fulfilling all criteria on a case by case basis. Any exceptions to the inclusion and exclusion criteria will be documented in writing and approved by Rhythm prior to dosing the patient.

4.2. Inclusion Criteria:

1. Bi-allelic, homozygous or compound heterozygous (a different gene mutation on each allele) genetic status for the *LEPR* gene, with the loss-of-function (LOF) variant for each allele conferring a severe obesity phenotype.
2. Age 6 years and above.
3. If adult age ≥ 18 years, obesity with $\text{BMI} \geq 30 \text{ kg/m}^2$; if child or adolescent, obesity with $\text{BMI} \geq 95\text{th percentile for age on growth chart assessment}$.
4. Study participant and/or parent or guardian is able to communicate well with the investigator, to understand and comply with the requirements of the study, and is able to understand and sign the written informed consent/assent, after being informed about the study.
5. Female participants of child-bearing potential must agree to use contraception as outlined in the protocol. Female participants of non-childbearing potential, defined as surgically sterile (status post hysterectomy, bilateral oophorectomy, or bilateral tubal ligation) post-menopausal for at least 12 months (and confirmed with a screening FSH level in the post-menopausal lab range), or have delayed pubertal development and failure to have achieved menarche, do not require contraception during the study.

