5.4. Blinding, Packaging, and Labeling

5.4.1. Blinding and Breaking the Blind

This study will be open label, except for the 8-week double-blind, placebo controlled variably timed withdrawal period. Blinding will be accomplished so that all patients and study-related staff remain blinded to study drug and patient assignment.

The Investigator, study site staff, clinical research organization staff providing site management and Medical Monitor will not have access to the actual treatment sequence being administered during the 8-week double-blind placebo controlled phase, except in the case of an emergency. Breaking the blind for a patient should be done only in the event of a medical emergency where the identity of study drug is necessary to appropriately treat the patient. The request to break the blind should be discussed with the Medical Monitor and Rhythm, whenever possible. If the blind is broken, the reason, when and how the blind was broken will be documented. Every attempt will be made to maintain the blind throughout the study.

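### Does the open-ended number of patients, with termination allowed once the data suffice, undermine the one-sided 0.05 level of the primary test?

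*Protocol*

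**What the plan says.** **Number of patients.** The synopsis (Number of Patients & Study Centers) anticipates about 10 and adds that "the total number of patients may be increased or decreased to satisfy regulatory requirements for registration", depending on how many affected patients are found. Section 4.1 reads "It is currently anticipated that at least 10 patients will be treated for ~1 year with setmelanotide". Section 2.1 says that "if additional patients are identified beyond the target enrollment of 10, they may be enrolled", and section 3.1 says much the same. No minimum or maximum is fixed.

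**Stopping.** Section 3.4 concedes that "it is still unclear how many patients will be required in a pivotal study" and draws from this that "this study may be terminated when Rhythm, in consultation with regulatory authorities, determines that there is sufficient patient data to support the potential application".

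**Visibility of results.** Section 5.4.1: "This study will be open label, except for the 8-week double-blind, placebo controlled variably timed withdrawal period". The 1-year weights are therefore unblinded.

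**Analysis.** Sections 8.1 and 8.2 test the proportion of the full analysis set (FAS) with at least 10% weight loss against a null of 5%, one-sided at 0.05, without adjustment. The FAS holds everyone dosed who has a baseline value. Patients with no data after month 10 count as non-responders. The synopsis gives the cut-off for N=10 only, as 3 responders. Section 8.3 places the analysis after the planned patients have completed about a year and the database is locked.

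**The concern.** Three features together look like uncontrolled optional stopping. N can move up or down without bounds, the sponsor can see who is responding, and one ground for ending the trial is a judgement that the data suffice. The safety monitoring board in section 7.3.1 also includes sponsor employees and may decide on termination.

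An exact binomial test holds its level when N is chosen without regard to the outcomes. If N follows the outcomes, the chance of a nominal p of 0.05 or less at some convenient N can be larger. This is the only confirmatory test of a pivotal single-arm trial, so an inflated level would weaken the main claim. The synopsis allows fewer than 10 patients and section 4.1 does not foresee that, so the text alone does not show which N values are in play.

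**Working it through.** **Inputs.** Null rate 0.05, one-sided alpha 0.05, unadjusted (sections 8.1, 8.2). Cut-off 3 of 10 (synopsis, Statistical Considerations). The N windows below are assumptions, because the protocol gives no bounds.

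**Step 1: reproduce the plan's figures.** With N=10 and success at X ≥ 3, P(X ≥ 3) is 0.322, 0.617, 0.833, 0.945 and 0.988 for true rates 0.2 to 0.6, matching the table in section 8.1. At the null:

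P(X ≥ 3 | 10, 0.05) = 1 − 0.5987 − 0.3151 − 0.0746 = 0.0115, and P(X ≥ 2 | 10, 0.05) = 0.0861.

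The cut-off of 3 is right, and it uses less than a quarter of the 0.05 allowed.

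**Step 2: cut-off at each N.** The smallest r with P(X ≥ r | N, 0.05) ≤ 0.05 is 2 for N = 2–7 (0.0444 at N=7), 3 for N = 8–16 (0.0429 at N=16) and 4 for N = 17–28 (0.0491 at N=28).

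**Step 3: worst case.** Take a true rate of exactly 5% and a sponsor who stops at the first N in the window where the test is significant. The probability that this ever happens bounds the level of any results-driven rule in that window.

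- *10 to 16.* The cut-off is 3 throughout, so crossing at any point is the same as having at least 3 of 16: 0.0429.
- *10 to 22.* Add the paths with fewer than 3 of 16 that reach 4 by N=22:
  P(X16=2)·P(Bin6 ≥ 2) + P(X16=1)·P(Bin6 ≥ 3) + P(X16=0)·P(Bin6 ≥ 4)
  = 0.1463×0.0328 + 0.3706×0.0022 + 0.4401×0.0001 ≈ 0.0057.
  Total 0.0429 + 0.0057 = 0.0486. Starting at 8 gives the same value.
- *10 to 23.* The same sum with 7 further patients is 0.0080, giving 0.0509, the first value above 0.05.
- *7 to 12.* 0.0444 + P(X7=1)·P(Bin5 ≥ 2) + P(X7=0)·P(Bin5 ≥ 3) = 0.0444 + 0.2573×0.0226 + 0.6983×0.0012 ≈ 0.0510.

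**Step 4: allow for the lag of a 1-year endpoint.** Each patient takes about 54 to 66 weeks (section 5.5), so some dosed patients would lack a 1-year weight at an early stop, and section 8.1 counts them as non-responders. Assume m such patients at every stop before the last N, and all complete at the last N:

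| Window of N | m=0 | m=1 | m=2 | m=4 |
|---|---|---|---|---|
| 7–12 | 0.051 | 0.042 | 0.035 | 0.024 |
| 7–16 | 0.069 | 0.061 | 0.055 | 0.047 |
| 7–20 | 0.070 | 0.059 | 0.048 | 0.032 |
| 10–23 | 0.051 | 0.046 | 0.042 | 0.036 |
| 10–28 | 0.069 | 0.065 | 0.062 | 0.057 |

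**Step 5: the null rate.** Section 8.1 argues that the untreated rate is 0% and sets 5% above that. If it were 1% (assumption), the zero-lag worst case would be 0.002 for 7–20 and 0.0006 for 10–28.

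**The case for a change.** The strongest reply is that error control should rest on the design, not on the sponsor's restraint. Sample size and grounds for termination are protocol content, so their looseness cannot simply be left to the SAP. Section 3.4 makes stopping depend on whether the data suffice, which is a judgement on accumulated data. Very wide windows do worse: 10–50 gives 0.093 and 3–50 gives 0.114. The synopsis also remarks that 3 of 10 meets 0.025 one-sided; with 0.025 cut-offs the worst case passes that level already for 10–16 (0.0254) and is 0.031 for 10–20. One sentence of commitment would cost nothing.

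Part of this stands. The sentence is absent, and no bound on N is written. But the declared test is at 0.05; the 0.025 remark describes what 3 of 10 happens to satisfy. The wide windows are remote, since section 2.1 reports that "there have been less than 50 cases currently described in the literature" and three body sections expect at least 10 patients. The stated reasons for changing N are regulatory need and the number of patients found, the decision on sufficiency is taken with regulators, and the board's data review is described as a safety assessment.

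A promise not to look is also hard to verify in an open-label trial. An enforceable alternative has a price. Limiting the confirmatory test to 8–22 patients would leave later FAS patients out of it, and requiring 3 responders at N=7 instead of 2 lowers power at a true 50% from 0.938 to 0.773.

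**Conclusion.** The concern does not call for a change. From N=10, the lowest figure anticipated in the body of the protocol, up to N=22, the exact test keeps its one-sided 0.05 level (at most 0.0486) under any choice of N, including one made with full sight of the responders. The reason is the slack from discreteness: the attained level at N=10 is 0.0115.

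Exceeding 0.05 needs either a test at 7 or fewer patients together with readiness to run to 12 or more, or a trial of 23 or more. The excess is then modest in windows of realistic width (0.051 to 0.070). It assumes a true untreated rate at the full 5%. It also assumes little outcome lag: with four incomplete patients at each stop, only 10–28 among the windows tabulated stays above 0.05.

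The mismatch between the synopsis and section 4.1 is between two forecasts, neither of which fixes N. Harmonising them, or noting that N is set without reference to responder results, would be optional tidying. It would not alter the analysis or the conclusion drawn from it. If N did end at 7 or fewer, or at 23 or more, how it was chosen would deserve a line in the study report.

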4. STUDY POPULATION

4.1. Number of Patients

It is currently anticipated that at least 10 patients will be treated for ~1 year with setmelanotide. Given the ultra-rare incidence of the disease, if additional patients are identified, they may be enrolled as available to gain additional experience. The study population will include obese males and females that are at least 6 years old with confirmed diagnosis of bi-allelic or loss-of-function *LEPR* loss of function gene mutation.

Given this study involves participants <18 years of age, measures should be taken to reduce pain and distress in this younger population. Considerations for the study staff are included in Appendix 11.11.

The specific inclusion and exclusion criteria for enrolling patients in this study are presented in the section below. As these patients are ultra-rare, any criteria not fulfilled will be reviewed with Rhythm. Assuming no severe health concerns, a joint determination will be made regarding the acceptability of enrolling patients not fulfilling all criteria on a case by case basis. Any exceptions to the inclusion and exclusion criteria will be documented in writing and approved by Rhythm prior to dosing the patient.

4.2. Inclusion Criteria:

1. Bi-allelic, homozygous or compound heterozygous (a different gene mutation on each allele) genetic status for the *LEPR* gene, with the loss-of-function (LOF) variant for each allele conferring a severe obesity phenotype.
2. Age 6 years and above.
3. If adult age ≥ 18 years, obesity with $\text{BMI} \geq 30 \text{ kg/m}^2$; if child or adolescent, obesity with $\text{BMI} \geq 95\text{th percentile for age on growth chart assessment}$.
4. Study participant and/or parent or guardian is able to communicate well with the investigator, to understand and comply with the requirements of the study, and is able to understand and sign the written informed consent/assent, after being informed about the study.
5. Female participants of child-bearing potential must agree to use contraception as outlined in the protocol. Female participants of non-childbearing potential, defined as surgically sterile (status post hysterectomy, bilateral oophorectomy, or bilateral tubal ligation) post-menopausal for at least 12 months (and confirmed with a screening FSH level in the post-menopausal lab range), or have delayed pubertal development and failure to have achieved menarche, do not require contraception during the study.
6. Male participants with female partners of childbearing potential must agree to a double barrier method if they become sexually active during the study. Male patients must not donate sperm during and for 90 days following their participation in the study.

4.3. Exclusion Criteria

1. Recent intensive (within 2 months) diet and/or exercise regimen with or without the use of weight loss agents including herbal medications, that has resulted in weight loss or weight stabilization. Patients may be reconsidered approximately 1 month after cessation of such intensive regimens.
2. Prior gastric bypass surgery resulting in $>10\%$ weight loss durably maintained from the baseline pre-operative weight with no evidence of weight regain. Specifically, patients may

be considered if surgery was not successful, or resulted in <10% weight loss compared to pre-operative baseline weight or clear evidence of weight regain after an initial response to bariatric surgery. All patients with a history of bariatric surgery must be discussed with, and receive approval from Rhythm prior to enrollment.

3. Diagnosis of schizophrenia, bipolar disorder, personality disorder or other Diagnostic and Statistical Manual of Mental Disorders (DSM-III) disorders that the investigator believes will interfere significantly with study compliance.
4. A Patient Health Questionnaire-9 (PHQ-9) score of ≥ 15 .
5. Any suicidal ideation of type 4 or 5 on the Columbia Suicide Severity Rating Scale (C-SSRS). Any lifetime history of a suicide attempt, or any suicidal behavior in the last month.
6. Current, severe stable restrictive or obstructive lung disease arising because of extreme obesity, evidence of significant heart failure (NYHA Class 3 or greater), or oncologic disease, if these were severe enough to interfere with the study and/or would confound the results. Any such patients should be discussed with the sponsor prior to inclusion.
7. History of significant liver disease or liver injury, or current liver assessment for a cause of abnormal liver tests [as indicated by abnormal liver function tests, alanine transaminase (ALT), aspartate transaminase (AST), alkaline phosphatase, or serum bilirubin ($> 2.0 \times$ upper limit of normal (ULN) for any of these tests)] for an etiology other than non-alcoholic fatty liver disease (NAFLD). Thus, any underlying etiology besides NAFLD, including diagnosed non-alcoholic steatohepatitis (NASH), other causes of hepatitis, or history of hepatic cirrhosis will be exclusionary, but the presence of NAFLD would not be exclusionary.
8. History or presence of impaired renal function as indicated by clinically significant abnormal creatinine, blood urea nitrogen (BUN), or urinary constituents (e.g., albuminuria) or moderate to severe renal dysfunction as defined by the Cockcroft Gault equation $< 30 \text{ mL/min}$ (Appendix 11.10).
9. History or close family history (parents or siblings) of skin cancer or melanoma, or patient history of ocular-cutaneous albinism.
10. Significant dermatologic findings relating to melanoma or pre-melanoma skin lesions, determined as part of a screening comprehensive skin evaluation performed by a qualified dermatologist. Any concerning lesions identified during the screening period will be biopsied and results known to be benign prior to enrollment. If the pre-treatment biopsy results are of concern, the patient may need to be excluded from the study.
11. Volunteer is, in the opinion of the Study Investigator, not suitable to participate in the study.
12. Participation in any clinical study with an investigational drug/device within 3 months prior to the first day of dosing.
13. Previous history of significant hypersensitivity to exogenously injected peptides (e.g. urticaria, shortness of breath, or more severe responses including anaphylactoid reactions or anaphylaxis).
14. Inability to comply with QD injection regimen.
15. Patients who have been placed in an institution through an official or court order, as well as those who are dependent on the sponsor, Investigator or study site.

